1.0 Synopsis

Title	Clostridium histolyticum collagenase injection treatment for urethral disease: a prospective pilot, single-center, open-label study
Protocol Number	CHC
Phase	II
Study Design	Pilot, open label drug study
Study Center(s)	Single-center (University of South Florida, Tampa, FL)
Objectives	
Primary Objectives
 
The primary objective is to assess the safety of clostridium histolyticum collagenase (XIAFLEX®) in treating urethral strictures.
 
Safety variable:
 
○ The primary safety variable will be complication rates following XIAFLEX® treatment Complications – specifically focus on pain, fever, genital lesions, or postoperative adverse events related to XIAFLEX® treatment 
Secondary Objectives
 
The secondary objectives are to assess the efficacy of XIAFLEX® treatment in improving obstructive voiding dysfunction, safety of XIAFLEX® administration into urethral strictures via a transurethral approach and the quality of life following XIAFLEX® treatment.
 
Secondary efficacy variables:
 
○ The percentage of subjects needing further intervention for treatment of urethral stricture during the 2 years follow-up Further intervention – defined as any medical or surgical intervention for treatment of urethral stricture.○ Urethral stricture recurrence during the 2 years follow-up○ Elapsed time to urethral stricture recurrence during the 2 years follow-up○ Elapsed time to additional intervention for urethral stricture treatment during the 2 years follow-up○ Improvement of obstructive voiding dysfunction – defined as change in uroflow and post-void residual measurements at baseline and 6-week post treatment and follow-up visits○ Quality of Life – change in AUA scores at baseline and 6-week post treatment and follow-up visits 
Secondary safety variable:
 
○ Spongiosis - incidence of formation of spongiosis or change in length and extent of spongiosis between

	
the baseline and follow-up visits on ultrasound and cystoscopic evaluation
 
 ○ Normal urethra proximal to injected tissue – incidence of change in normal urethra structure proximal to injected tissue between baseline and follow-up visits
Number of Subjects	5 Patients
Inclusion Criteria	
 1) Males 2) Age \geq 18 years 3) Failed prior proven conservative measures, including DVIU or balloon dilation of the stricture will be included in this study 4) Able and willing to undergo regular intervention as well as evaluation as described below will be included in the study 5) With a single bulbar stricture \leq 2cm in size that can be identified on retrograde urethrogram or voiding cystourethrogram and visible with urethral ultrasonography will be included in the study. 6) Must agree not to participate in a clinical study involving another investigational drug or device throughout the duration of this study 7) Must be competent to understand the information given in IRB approved ICF and must sign the form prior to the initiation of any study procedure
Exclusion Criteria	
 1) Has not yet undergone proven non-invasive measures, including DVIU or balloon dilation. 2) Multiple strictures or a single stricture larger than 2cm in size, measured with retrograde urethrogram, voiding cystourethrogram, or urethral ultrasonography. 3) Corporal spongiosum tissues $<$ 5 mm in depth at proposed injection site 4) Grade 5 spongiositis 5) Age $<$ 18 6) Females 7) Prior urethroplasty 8) Urethral fistula 9) History of penile cancer, prostate cancer, or urinary tract malignancy (bladder, urethral, ureteral, or kidney). 10) History of radiation (external or brachytherapy) to the pelvic organs, penis or groin. 11) History of autoimmune or inflammatory bowel disease 12) Contraindication to suprapubic tube placement 13) Pre-procedure PVR $>$ 250mL 14) Allergy or sensitivity to CHC 15) Bleeding disorder or anticoagulant use other than aspirin up to 150mg/day

	
16) Untreated or recurrent urinary tract infection 17) Inability to perform intermittent self-catheterization 18) Participation in another clinical study or treatment with an investigational drug or device 19) Serious or active medical or psychiatric condition which, in the opinion of the Investigator, may interfere with treatment, assessment, or compliance with the protocol

Study Product, Dose, Route, Regimen	
Patients will first be identified and evaluated with fluoroscopic and ultrasound imaging. Based on the inclusion and exclusion criteria they will be counseled about eligibility for the study along with discussion of standard management options and possible risks of the investigation including full informed consent.
 
On day of treatment, patients will undergo instillation of local anesthesia (20 mL of 2% urethral lidocaine jelly), the patient will undergo cystoscopy, transurethral injection (via a 70 cm 4.8 Fr flexible cystoscopic needle with a 23 gauge needle tip manufactured by Laborie®, Ontario, Canada) of 0.08ml of XIAFLEX® (0.58 mg of XIAFLEX® mixed with 0.39 mL of sterile diluent) in a single location within the stricture, chased by an additional 0.25 mL of reconstituted XIAFLEX® to allow for clearance of the original 0.08 mL of reconstituted XIAFLEX® from the transurethral syringe into the urethral stricture. This is based on 0.25 mL residual fluid that remains within the lumen of the injeTAK syringe. Thus, by adding the additional 0.25 mL of XIAFLEX® as a chase, we are expecting the original total of 0.08 mL of XIAFLEX® to be injected into the area of scarring. The depth and location of the needle will be determined pre-procedurally with urethral ultrasonography with the needle in a semi-parallel manner into the plaque as to avoid perforation into nearby structures. Injections will be performed at a single site identified on ultrasound as appropriate, and avoiding the 6 o'clock and 12 o'clock sites where potential perforation can lead to additional complications. The site of injection will be recorded accordingly for safety monitoring following treatment. The remaining 0.25 mL that remains in the injection syringe will be discarded per institutional policy for biohazard disposal.

Statistical Methodology	
Data analysis will be conducted using de-identified data in SPSS or SAS statistical software.
 
Study Population Analysis The distributions of the following characteristics will be tabulated and presented with descriptive statistics (i.e. mean, standard deviation, median, minimum, maximum, and patient count for continuous variables, and counts with percentages for categorical variables):
 
 - Demographics - Medical and surgical history - Final study exit classification (completed, discontinued, withdrew)

Primary Safety Endpoint

2.0 Background

2.1 Urethral Stricture Disease

Urethral stricture disease can be difficult and expensive problem for urologists to manage. The total cost of urethral stricture diseases in 2000 was approximately \$200 million. A diagnosis of urethral stricture increased health care expenditures by more than \$6,000 per individual yearly¹. Conservative management involves frequent straight catheterization or management with an indwelling foley catheter; options that can decrease the patient's quality of life and increase the patient's risk of urinary tract infections².

2.1.1 Treatment of Urethral Stricture

Minimally invasive treatment options include direct vision internal urethrotomy (DVIU) and urethral dilation; these have been shown to be effective primarily on single, small bulbar strictures (<2cm), with repeated treatment being almost entirely ineffective³. Other minimally invasive treatments including urethral stents, transurethral injection with Rapamycin, botulinum toxin, or glucocorticoids have shown limited efficacy or have fallen out of favor because of increased morbidity^{4,5}. The gold standard for treatment of anterior urethral strictures involves excision of the stricture with primary anastomosis of the urethra or urethroplasty. Both surgical options, however, require extensive anesthesia and are often poor options for elderly patients, patients with significant comorbidities, or patient who simply do not wish to undergo such extensive surgery.

2.2 *Clostridium Histolyticum Collagenase*

Clostridium histolyticum collagenase (CHC) is an injectable pharmacologic agent that works by hydrolyzing collagen under physiologic environments, with in vitro studies showing CHC to be specifically selective for collagen type I and III, the predominant types found in Peyronie's plaque's and Dupuytren's contractures. Additionally, CHC spares collagen type IV, which is present within connective tissue of surrounding arteries, large veins, and nerves, limiting surrounding nerve or vessel damage⁶. CHC, marketed as XIAFLEX®, has been FDA approved for treatment of Dupuytren's disease, as well as Peyronie's disease. Large double blind studies have shown a statistically significant improvement in penile deformity following CHC injections⁷. Additionally, studies have shown significant improvement in curvature in patients who performed penile modeling with CHC.

2.2.1 Animal Studies: Toxicity Data

Based on a previously conducted study on local toxicity of Auxilium's collagenase (AA4500) injected into various locations within the dogs penis, including the urethra, primary side effects were dose related and included discoloration of the penis/prepuce, persistence of swollen penis, and bruising.⁸ At a dose of 6.1 µg/kg, which corresponds to 1.1 fold on the mg/kg basis of the human dose, 4 out of 6 dogs were able to receive all three doses (total 3 dosing cycles). The primary toxicity findings at all dose levels were hemorrhage, edema, necrosis, inflammation, and neovascular proliferation with increasing severity based on dosing.

Histopathology indicated resolution was in progress at the end of the 28-day treatment-free period. There was no significant systemic toxicity following intrapenile injections. Necrosis did not affect non-collagenous strictures within or adjacent to the injected tissue, nor was there any evidence of residual effects on these structures in recovery animals in all phases of the study. In particular, arteries, veins, nerves, and large veins were unaffected, with necrosis only seen in smaller veins comprised mostly of collagen and minimal smooth muscle.

Antibodies to AA4500 were detected in all repeat-dose dogs following their last dose on Day 61. The consequence of antibody formation is unknown. However, the author did note that the presence of antibodies did not result in any apparent adverse systemic effects. Nor did the production of antibodies appear to alter the toxicokinetics or pharmacodynamics effects of aA4500.

In another animal study, injecting clostridial collagenase (both 150 units and 300 units injected) into rats tail tendon showed local collagen lysis of injection at the site of injection only at 1 and 24 hours.⁹ At both doses, no adverse collagenase extravasation was seen at either time at the injection site or 0.5 cm proximal or distal to the injection site.

2.3 Rationale for Urethral Stricture Treatment with XIAFLEX®

Urethral strictures, like Dupuytren's contractures and Peyronie's disease, are associated with a total increase in type I and type III collagen smooth muscle¹⁰. A recent study investigated injecting urethral strictures with high dose CHC in rats showed reduction in urethral fibrosis as well as a reduction in collagen type I and III expression in the rodents' urethral strictures¹¹. We wish to investigate if CHC would have a similar impact on urethral strictures in men when administered in a similar fashion to the Peyronie's disease algorithm.

3.0 Study Objectives

We hypothesize that XIAFLEX® (Endo Pharmaceuticals, Dublin, Ireland) injection is an effective treatment for urethral strictures.

Primary Objectives

The primary objective is to assess the safety of clostridium histolyticum collagenase (XIAFLEX®) in treating urethral strictures.

Safety variable:

- The primary safety variable will be complication rates following treatment (XIAFLEX®)
Complications – specifically focus on pain, fever, genital lesions, or postoperative adverse events related to treatment (XIAFLEX®)

Secondary Objectives

The secondary objectives are to assess the efficacy of XIAFLEX® treatment in improving obstructive voiding dysfunction, safety of XIAFLEX® administration into urethral strictures via a transurethral approach and the quality of life following XIAFLEX® treatment.

Secondary efficacy variables:

- The primary efficacy variable will be the percentage of subjects needing further intervention for treatment of urethral stricture during the 2 years follow-up

- Further intervention – defined as any medical or surgical intervention for treatment of urethral stricture.
- Urethral stricture recurrence during the 2 years follow-up
- Elapsed time to urethral stricture recurrence during the 2 years follow-up
- Elapsed time to additional intervention for urethral stricture treatment during the 2 years follow-up
- Improvement of obstructive voiding dysfunction – defined as change in uroflow and post-void residual measurements at baseline and 6-week post treatment and follow-up visits
- Quality of Life – change in AUA scores at baseline and 6-week post treatment and follow-up visits

Secondary safety variables:

- Spongiosclerosis - incidence of formation of spongiosclerosis or change in length and extent of spongiosclerosis between the baseline and follow-up visits
- Normal urethra proximal to injected tissue – incidence of change in normal urethra structure proximal to injected tissue between baseline and follow-up visits

4.0 Study Population

Male patients receiving treatment at USF for obstructive voiding symptoms or catheter dependent because of urethral stricture disease.

4.1 Inclusion Criteria

Patients must meet all of the following inclusion criteria to be eligible for participation in this study.

- 1) Males
- 2) Age \geq 18 years
- 3) Failed prior proven conservative measures, including DVIU or balloon dilation of the stricture will be included in this study
- 4) Able and willing to undergo regular intervention as well as evaluation as described below will be included in the study
- 5) With a single bulbar stricture \leq 2cm in size that can be identified on retrograde urethrogram or voiding cystourethrogram and visible with urethral ultrasonography will be included in the study will be included in the study.
- 6) Must agree not to participate in a clinical study involving another investigational drug or device throughout the duration of this study
- 7) Must be competent to understand the information given in IRB approved ICF and must sign the form prior to the initiation of any study procedure

4.2 Exclusion Criteria

Patients who meet any of the following exclusion criteria are not eligible for participation in this study.

- 1) Has not yet undergone proven non-invasive measures, including DVIU or balloon dilation.

- 2) Multiple strictures or a single stricture larger than 2cm in size, measured with retrograde urethrogram, voiding cystourethrogram, or urethral ultrasonography.
- 3) Corporal spongiosum tissues < 5 mm in depth at proposed injection site
- 4) Grade 5 spongiosfibrosis
- 5) Age <18
- 6) Females
- 7) Prior urethroplasty
- 8) Urethral fistula
- 9) History of penile cancer, prostate cancer, or urinary tract malignancy (bladder, urethral, ureteral, or kidney).
- 10) History of radiation (external or brachytherapy) to the pelvic organs, penis or groin.
- 11) History of autoimmune or inflammatory bowel disease
- 12) Contraindication to suprapubic tube placement
- 13) Pre-procedure PVR >250mL
- 14) Allergy or sensitivity to CHC
- 15) Bleeding disorder or anticoagulant use other than aspirin up to 150mg/day
- 16) Untreated or recurrent urinary tract infection
- 17) Inability to perform intermittent self-catheterization
- 18) Participation in another clinical study or treatment with an investigational drug or device
- 19) Serious or active medical or psychiatric condition which, in the opinion of the Investigator, may interfere with treatment, assessment, or compliance with the protocol

5.0 Study Drug and Device

5.1 Study Agent

XIAFLEX® is a combination of bacterial collagenases indicated for the treatments of adult patients with Dupuytren's contracture with a palpable cord and adult men with Peyronie's disease with a palpable plaque and curvature deformity of at least 30 degrees at the start of therapy. XIAFLEX® contains purified collagenase clostridium histolyticum, consisting of two microbial collagenases in a defined mass ratio, Collagenase AUX-I and Collagenase AUX-II, which are isolated and purified from the fermentation of Clostridium histolyticum bacteria. The dosing used for this study is based on recommendations for Peyronie's disease treatment with XIAFLEX®.

5.2 Dose Rationale

A recently published comprehensive review of recent clinical trials and in vivo studies examining CHC in the treatment of Peyronie's disease reported that the clinical trials have demonstrated the efficacy and tolerability of CHC in treating Peyronie's disease and an in vivo study showed that CHC also could be applied to urethral stricture disease without serious adverse complications.¹² A recent urethral injection of rat model (300-350g) used 0.05 - 0.1mg CCH per subject. This showed no urethral or voiding complication and no urinary retention or urethral fistulas¹¹. This dosing would equal 0.14-0.33mg/kg. A dose of 0.119mg (0.08ml of 0.58mg XIAFLEX in 0.39ml) in a 70kg patient would be 0.0017mg/kg.

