5.4 Dosage and Administration

On day of treatment, prior to study drug administration, photographic evidence captured with urethral ultrasound will be used to confirm eligibility criterion: < Grade 5 spongiosis. If the patient's urethral ultrasound for Baseline/Screening was performed more than 30 days prior to the treatment day (Day 0), it will be performed again on the treatment day (Day 0) prior to study drug administration to re-confirm the patient's study eligibility and to allow for proper procedural planning for study treatment.

On day of treatment, patients will undergo instillation of local anesthesia (20 mL of 2% urethral lidocaine jelly), the patient will undergo cystoscopy, transurethral injection (via a 70 cm 4.8 Fr flexible cystoscopic needle with a 23 gauge needle tip manufactured by Laborie®, Ontario, Canada) of 0.08ml of XIAFLEX® (0.58 mg of XIAFLEX® mixed with 0.39 mL of sterile diluent) in a single location within the stricture, chased by an additional 0.25 mL of reconstituted XIAFLEX® to allow for clearance of the original 0.08 mL of reconstituted XIAFLEX® from the transurethral syringe into the urethral stricture. This is based on 0.25 mL residual fluid that remains within the lumen of the injeTAK syringe. Thus, by adding the additional 0.25 mL of XIAFLEX® as a chase, we are expecting the original total of 0.08 mL of XIAFLEX® to be injected into the area of scarring. The depth and location of the needle will be determined procedurally with urethral ultrasonography with the needle in a semi-parallel manner into the plaque as to avoid perforation into nearby structures. Injections will be performed at a single site identified on ultrasound as appropriate, and avoiding the 6 o'clock and 12 o'clock sites where potential perforation can lead to additional complications. The site of injection will be recorded accordingly for safety monitoring following treatment. The remaining 0.25 mL that remains in the injection syringe will be discarded per institutional policy for biohazard disposal.

Reconstitution of the Lyophilized Powder for Peyronie's Disease (taken from XIAFLEX® package insert)

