1. Before use, remove the vial containing the lyophilized powder of XIAFLEX® and the vial containing the diluent for reconstitution from the refrigerator and allow the two vials to stand at room temperature for at least 15 minutes and no longer than 60 minutes. Visually inspect the vial containing XIAFLEX®. The cake of lyophilized powder should be intact and white in color.
2. After removal of the flip-off cap from each vial, using aseptic technique swab the rubber stopper and surrounding surface of the vial containing XIAFLEX® and the vial containing the diluent for reconstitution with sterile alcohol (no other antiseptics should be used).

3. Use on the supplied diluent for reconstitution. The diluent contains calcium which is required for the activity of XIAFLEX®.
4. Using a 1 mL syringe with 0.01 mL graduations with a 27-gauge ½-inch needle, withdraw a volume of 0.39 mL of the diluent supplied.
5. Inject the diluent slowly into the sides of the vial containing the lyophilized powder of XIAFLEX®. Do not invert the vial or shake the solution. Slowly swirl the solution to ensure that all of the lyophilized powder has gone into solution.
6. The reconstituted XIAFLEX® solution can be kept at room temperature (20° to 25°C/68° to 77°F) for up to one hour or refrigerated at 2° to 8°C (36° to 46°F) for up to 4 hours prior to administration. If the reconstituted XIAFLEX® solution is refrigerated, allow this solution to return to room temperature for approximately 15 minutes before use.
7. Discard the syringe and needle used for reconstitution and the diluent vial.

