5.5 Formulation

XIAFLEX® will be supplied in single-use glass vials containing 0.9 mg of collagenase clostridium histolyticum as a sterile, lyophilized powder for reconstitution. Sterile diluent for reconstitution will be provided in a package in a single-use glass vial containing 3 mL of 0.3 mg/mL calcium chloride dehydrate in 0.9% sodium chloride.

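### The stated dose of 0.119 mg contradicts the protocol's own vial strength and reconstitution steps, which put 0.185 mg (55% more) in the same 0.08 mL

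*Combined protocol and SAP*

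**What the plan says.** Section 5.2 (Dose Rationale) states the dose in milligrams and per kilogram: "A dose of 0.119mg (0.08ml of 0.58mg XIAFLEX in 0.39ml) in a 70kg patient would be 0.0017mg/kg". It sets this against rat doses of 0.14 to 0.33 mg/kg.

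Section 5.4 (Dosage and Administration) describes the injected solution in the same terms, as "0.58 mg of XIAFLEX® mixed with 0.39 mL of sterile diluent", with 0.08 mL going into the stricture. The synopsis (section 1.0) and section 6.5.2 repeat this.

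Two other parts of the protocol describe how that solution is made:

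- Section 5.5 (Formulation): "XIAFLEX® will be supplied in single-use glass vials containing 0.9 mg of collagenase clostridium histolyticum as a sterile, lyophilized powder for reconstitution".
- The reconstitution steps in section 5.4: "withdraw a volume of 0.39 mL of the diluent supplied", then "Inject the diluent slowly into the sides of the vial containing the lyophilized powder of XIAFLEX", then "Slowly swirl the solution to ensure that all of the lyophilized powder has gone into solution".

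Section 5.6 adds that the product is used in its marketed packaging without modification, so the protocol provides for no special 0.58 mg vial.

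**The concern.** The dosing text and the preparation text describe two different solutions. One has 0.58 mg in 0.39 mL. The other has the whole 0.9 mg vial in 0.39 mL. With the diluent volume fixed at 0.39 mL and the injected volume at 0.08 mL, the milligram dose depends entirely on which mass is dissolved, and the protocol gives two values for it.

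The primary objective is safety, in five patients at one dose level and by a new route. A site that follows the written steps gives every patient a milligram dose that the protocol neither states nor uses in its rationale. The data and safety monitoring board would judge complications, and the final report would present them, against a dose about a third lower than the one given (0.119/0.185 = 0.64). A later study that took 0.119 mg as the tolerated dose would start from the wrong figure.

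**Working it through.** **Inputs**

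| Quantity | Value | Where |
|---|---|---|
| Drug mass in the dosing text | 0.58 mg | Sections 1.0, 5.2, 5.4, 6.5.2 |
| Drug mass in the vial | 0.9 mg | Section 5.5 |
| Diluent volume | 0.39 mL | Section 5.4, dosing text and reconstitution steps |
| Injected volume | 0.08 mL | Sections 1.0, 5.2, 5.4, 6.5.2 |
| Body weight | 70 kg | Section 5.2 |
| Rat doses | 0.14 to 0.33 mg/kg | Section 5.2 |
| Dog dose | 6.1 µg/kg | Section 2.2.1 |

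**Formula.** Dose = (drug mass / diluent volume) × injected volume. Dose per kg = dose / 70.

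**Step 1: reproduce the stated figure.** 0.58/0.39 = 1.487 mg/mL. Then 1.487 × 0.08 = 0.119 mg, and 0.119/70 = 0.0017 mg/kg. Both figures in section 5.2 reproduce, so the multiplication is sound and the question is whether 0.58 mg is the right input.

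**Step 2: use the vial and the preparation steps.** 0.9/0.39 = 2.308 mg/mL. Then 2.308 × 0.08 = 0.1846 mg, and 0.1846/70 = 0.00264 mg/kg. The ratio to the stated dose is 0.9/0.58 = 1.55.

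**Step 3: see whether the two descriptions can be reconciled.**

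- To reach 1.487 mg/mL from a 0.9 mg vial, the solution volume would have to be 0.9/1.487 = 0.605 mL. The steps add 0.39 mL.
- To deliver 0.119 mg at 2.308 mg/mL, the injected volume would have to be 0.119/2.308 = 0.052 mL. The protocol says 0.08 mL.
- No step uses part of the powder or dilutes the solution further.

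So 0.119 mg, 0.08 mL, 0.39 mL and a 0.9 mg vial cannot all be right.

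**Step 4: effect on the animal comparisons.**

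| Comparator | At the stated dose | At 0.185 mg |
|---|---|---|
| Rat, low (0.14 mg/kg) | 0.14/0.0017 = 82 fold | 0.14/0.00264 = 53 fold |
| Rat, high (0.33 mg/kg) | 0.33/0.0017 = 194 fold | 0.33/0.00264 = 125 fold |
| Dog (6.1 µg/kg) | 6.1/1.70 = 3.6 fold | 6.1/2.64 = 2.3 fold |

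Section 5.2 does not make the dog comparison. It is shown because section 2.2.1 reports local hemorrhage, edema and necrosis at all dog dose levels, so that is where the margin is narrowest.

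**Step 5: a possible origin of 0.58 mg.** At 2.308 mg/mL, 0.25 mL holds 2.308 × 0.25 = 0.577 mg. The content of 0.25 mL may have been taken for the content of the full 0.39 mL. This is an inference that the documents do not confirm, and the finding does not rest on it.

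**The case against.** The best defence is that the slip changes little in practice. The volume, 0.08 mL at one site, is stated consistently, so patients would be dosed alike, and only the milligram equivalent is misstated. No endpoint or analysis in section 6.7 uses milligrams or mg/kg, so the observed complication rate would not change. Section 5.8 requires records of product use by each patient, so the true dose could be worked out later. The rat comparison is also not the only support: section 5.1 bases the dosing on recommendations for Peyronie's disease, and section 2.2.1 adds dog data. Even at 0.0026 mg/kg the dose is more than 50 fold below the lowest rat dose and less than half of the 6.1 µg/kg dog dose.

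All of this is correct, and it limits the consequences: the safety argument keeps its direction and no test result changes. It is also fair to call the fault an inconsistent input and not a multiplication error. One larger-looking comparison should be kept apart: the 0.33 mL loaded (0.08 mL plus the 0.25 mL chase) holds 0.76 mg at 2.308 mg/mL, against 0.49 mg at 1.487 mg/mL. That is drug in the device, and the protocol expects only 0.08 mL to reach tissue.

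None of these points reconciles 0.58 mg with 0.9 mg. The stated dose remains wrong for the solution that the steps produce.

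**Conclusion.** The concern holds. Prepared as written, the solution is 2.31 mg/mL, and 0.08 mL holds 0.185 mg (0.0026 mg/kg at 70 kg), not 0.119 mg (0.0017 mg/kg). The true dose is 1.55 times the stated one.

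This rests on three assumptions: the vial holds its labelled 0.9 mg, the powder adds no appreciable volume to the 0.39 mL, and 0.08 mL is the volume delivered. The powder would have to bring the volume to about 0.605 mL to rescue the stated dose, which 0.9 mg cannot do.

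The rationale survives with smaller margins. The dose itself is wrong as written and must be corrected, because in a single-dose safety trial it is the exposure to which every safety result refers.

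**What to change.** The sponsor first decides which quantity was intended.

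- **If 0.08 mL was intended:** replace the 0.58 mg in 0.39 mL description in sections 1.0, 5.2, 5.4 and 6.5.2 with 0.9 mg in 0.39 mL (2.31 mg/mL). Restate section 5.2 as 0.185 mg and 0.0026 mg/kg. The cost is an amendment to the text, and the margin to the animal data becomes less favourable.
- **If 0.119 mg was intended:** either inject about 0.052 mL of the 2.31 mg/mL solution, or reconstitute to about 0.605 mL and keep 0.08 mL. This is an operational change. The first option needs a syringe that measures so small a volume reliably; the second departs from the package-insert preparation that section 5.4 reproduces.

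In either case, state the concentration in mg/mL wherever the dose appears, and check that vial content, diluent volume, injected volume, milligrams and mg/kg agree across sections 1.0, 5.2, 5.4, 5.5 and 6.5.2. Give the corrected dose to the monitoring board and use it in the report. If anyone has already been treated, recalculate the dose received from the preparation records. No change to sample size or analysis is needed.
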